4.0 Study Endpoints

- 4.1 Time to perform each block.
- 4.2 Pain scores and opioid consumption during the first 24 and 48 hours post-op.

5.0 Study Intervention/Investigational Agent

- 5.1 Study subjects will receive either a LPB or a suprainguinal FICB under ultrasound guidance. Either block will be achieved with 3 mg/kg (0.6 mL/kg) of ropivacaine 0.5% with 1:200,000 epinephrine.
- 5.2 Both of these blocks are considered standard of care and patients could receive either one without participating in this study.

6.0 Procedures Involved*

- 6.1 This will be a double-blinded, randomized, prospective study involving patients, ranging in age between 2 and 18 years of age, ASA grade I-III, undergoing elective orthopedic surgical procedures involving the hip and upper thigh. Patients will be randomly divided into 2 groups: Group LP and Group FICB. The block (LP or FICB) will be performed by one of the study investigators. The team providing intraoperative care will step out of the room during the regional block and care will be provided by the research team including an attending anesthesiologist. Once the primary anesthesia team finishes the induction phase, the study team will perform the regional anesthesia time-out. Measurement of the time to complete the block will start when the time-out is completed and end when the need is withdrawn and the patient is positioned in the surgical positioning. The perioperative care teams will be blinded to the type of the block by using two dressings in all the patients. The first dressing will be placed at the actual site of needle insertion and the second dressing at the site where needle would have been inserted if the patient were to receive the other type of block (in the back for the LP block and groin for the FICB).
- 6.2 Anesthetic care will be standardized in all patients except for type of the regional nerve block. Patients requiring anxiolysis will receive oral midazolam 0.3-0.5 mg/kg (maximum 20 mg) 30 minutes prior surgery or intravenous midazolam (0.05 mg/kg up to 2 mg) prior to transport to the operating room. Once in the operating room, all patients will be monitored as per standard ASA guidelines. Anesthetic induction will be achieved with 70% nitrous oxide in oxygen and sevoflurane or with intravenous propofol. If preoperative midazolam was not administered, intravenous midazolam will be administered (0.05 mg/kg to a maximum of 2 mg). Following loss of consciousness, fentanyl (2 μ g/kg) will be administered and the trachea intubated. Administration of neuromuscular blocking agents (NMBA) will be deferred until after regional anesthesia technique has been performed. Rocuronium (0.6-1 mg/kg) will be used according to surgeons request. In case NMBA are needed for tracheal intubation then succinylcholine (1-2mg/kg) will be used. Anesthesia will be maintained with 1-2 MAC of sevoflurane in 50% oxygen/air. Following endotracheal intubation, patients will receive either a LPB or a suprainguinal FICB under ultrasound guidance. Either block will be achieved with 3 mg/kg (0.6 mL/kg) of ropivacaine 0.5% with 1:200,000 epinephrine. Maximum block volume will be 30 mL for both blocks. The time from the initiation of the time-out for the block until the patient has been returned to the surgical position will be noted. Additional intraoperative analgesia will be achieved with bolus doses of fentanyl 1 μ g/kg to maintain the

PROTOCOL TITLE: LPB vs FICB

heart rate and blood pressure within 20% of baseline. Prophylaxis for postoperative nausea and vomiting will include dexamethasone (0.1-0.15 mg/kg up to 8 mg) and ondansetron (0.1-0.15 mg/kg up to 4 mg). At the conclusion of surgery, residual neuromuscular blockade will be reversed and the patient's trachea extubated.

6.3 Postoperative analgesia will be achieved with IV hydromorphone as needed (PRN) with a dose regimen of 0.02 mg/kg per dose. Depending on patient's use if there is need to escalate treatment a PCA, NCA or CCA will be started. Patients will also receive IV acetaminophen 15 mg/kg every 6 hours and IV ketorolac 0.5 mg/kg every 6 hours (unless contraindicated) during the 48 hour study period. The first dose of these two agents will be administered in the operating room at the completion of the surgical procedure. If the patient is ready to transition from IV to oral pain medications, oxycodone (0.1 mg/kg every 4 hours) will be started and the hydromorphone discontinued. At that time, acetaminophen will be switched to oral and ketorolac switched to oral ibuprofen.

6.4 The following data will be collected:

- Block procedure time (in minutes and seconds)
- Opioid administration intraoperatively.
- Postoperative opioid consumption in the PACU.
- Postoperative opioid consumption for the first 48 hours after surgery (PACU discharge to inpatient ward admission).
- Pain assessment scores (VAS in older children, FACES scales in children between 2-4 and FLACC for non-verbal children) in the PACU (first pain score) and for the first 48 hours (standard pain assessments) on the inpatient ward.
- The duration of the need for intravenous opioid therapy.
- Use of rescue pain medications in the PACU, on the floor, including non-opioids, will also be recorded and analyzed.
- Hospital length of stay.

The following demographic and surgical parameters will also be collected and recorded: patient age, gender, race/ethnicity, height, weight, ASA status, primary diagnosis, list of comorbidities, procedure, date, duration, admission status intraoperative medications, PACU arrival and discharge times, discharge destination, pain scores (including recorded time),

PROTOCOL TITLE: LPB vs FICB

regional anesthetic time and dose, and time of hospital admission and discharge.

7.0 **Data and Specimen Banking***

N/A

8.0 **Sharing of Results with Subjects***

8.1 Results will not be shared.

9.0 **Study Timelines***

- An individual study subject's participation in the study should last approximately 48 hours total.
- All study subjects should be enrolled within 2 years of study start.
- The study should be completed within 3 years of study start.

10.0 **Inclusion and Exclusion Criteria***

10.1 Potential subjects will be identified by reviewing the surgery schedule in Epic and will be recruited from the Surgery Unit pre-op area prior to their surgery.

10.2 Inclusion criteria: Aged 2-18 years, ASA grade 1-3, undergoing elective orthopedic surgical procedures involving the hip and upper thigh.

Exclusion criteria: Local anesthetic allergy, skin or localized infection at the site of catheter insertion opioid use within 3 months prior to surgery, history of opioid abuse or dependence, pre-existing motor or sensory deficits, patient or parent refusal.

10.3 We are including children, and will not include:

- Adults unable to consent
- Pregnant women
- Prisoners

11.0 **Vulnerable Populations***

11.1 This study presents no more than minimal risk as it involves regional nerve blocks which are used routinely as standard of care by the anesthesiologists at this institution.

12.0 **Local Number of Subjects**

12.1 70

12.2 Sample size will be determined according to a previous study investigating the time taken to perform 2 variations on the lumbar plexus block, with the slower technique taking 334 ± 156 seconds and the faster technique taking 238 ± 74 seconds. We hypothesize that the time difference between the 2 techniques in our study will be

PROTOCOL TITLE: LPB vs FICB

at least as large as the difference between the 2 block types investigated in this prior study. Specifically, assuming that the FICB will be at least 96 seconds faster than the LP block while the pooled standard deviation is 128 seconds, the proposed t-test would have 80% power to confirm a statistically significant difference at a 95% confidence level when at least 29 subjects are enrolled in each group. Therefore, we propose enrolling a total of 70 patients to account for dropout or missing data.

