2.0 Objectives

- 2.1 The primary objective will be to measure total time to perform the regional anesthesia technique. The secondary objectives are opioid consumption during the first 24 and 48 postoperative hours, pain scores during the first 24 and 48 hours, and hospital length of stay.
- 2.2 The hypothesis is that the two techniques will be equally effective in providing analgesia following hip and femur surgery in the pediatric population; however, the time to perform the FICB will be shorter than the lumbar plexus block.

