17.0 Data Management* and Confidentiality

17.1 Continuous outcomes will be compared between groups using 2-sample t-test or rank-sum tests according to the normality of the distribution (checked by the Shapiro-Wilk test). Categorical outcomes will be compared between groups using Chi-square or Fisher's exact tests, according to cell size.

17.2 Research records will be stored in a locked cabinet and password protected computer. Only certified research personnel will be given access to identifiable subject information

PROTOCOL TITLE: LPB vs FICB

17.3 Following publication of study results, research records will be stored for a period of 3-5 years and then will be destroyed by placing in a secure shredding bin.

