4.0 Describe any plans to code identifiable information collected about each participant. None

5.0 Check each box that describes steps that will be taken to safeguard the confidentiality of information collected for this research:

- Research records will be stored in a locked cabinet in a secure location
- Research records will be stored in a password-protected computer file
- The list linking the assigned code number to the individual subject will be maintained separately from the other research data
- Only certified research personnel will be given access to identifiable subject information

6.0 Describe the provisions included in the protocol to protect the privacy interests of subjects, where "privacy interests" refer to the interest of individuals in being left alone, limiting access to them, and limiting access to their information. (This is not the same provision to maintain the confidentiality of data.)
Subject information will not be given to any other investigators. Subjects and their information will be closely monitored and guarded by study staff; there will be limited access to patients and their information by trained study staff; and subject information will only be shared and discussed between study staff specific to this study.

Confidential Health Information

1.0 Please mark all categories that reflect the nature of health information to be accessed and used as part of this research.

- Demographics (age, gender, educational level)
- Diagnosis
- Laboratory reports
- Radiology reports
- Discharge summaries
- Procedures/Treatments received
- Dates related to course of treatment (admission, surgery, discharge)
- Billing information
- Names of drugs and/or devices used as part of treatment
- Location of treatment

PROTOCOL TITLE: LPB vs FICB

- Name of treatment provider
- Surgical reports
- Other information related to course of treatment
- None

2.0 Please discuss why it is necessary to access and review the health information noted in your response above.

It is necessary to meet the objectives of the study and to analyze the data.

3.0 Is the health information to be accessed and reviewed the minimal necessary to achieve the goals of this research? Yes No

4.0 Will it be necessary to record information of a sensitive nature? Yes No

5.0 Do you plan to obtain a federally-issued Certificate of Confidentiality as a means of protecting the confidentiality of the information collected? Yes No

References:

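### Block time depends partly on the operator, but the plan does not say whether the operator is chosen before allocation is known, does not list operator as data and does not use it in the analysis

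*Combined protocol and SAP*

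**What the plan says.** All references are to the combined protocol and SAP.

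- **Outcome.** Section 2.1: "The primary objective will be to measure total time to perform the regional anesthesia technique". Under 6.1 the clock stops once the needle is out and the patient is in position for surgery.
- **Allocation.** Section 6.1: "Patients will be randomly divided into 2 groups: Group LP and Group FICB". No stratification is described, and nothing says when the allocation is opened relative to the choice of operator.
- **Operator.** Section 6.1: "The block (LP or FICB) will be performed by one of the study investigators". The number of operators, their experience with each block and the rule for assigning them to cases are not given. Section 25.1 promises training in the study procedures but sets no level of block experience.
- **Data.** Section 6.4 lists the block procedure time and, among the surgical parameters, "regional anesthetic time and dose, and time of hospital admission and discharge". Operator is not listed. The health-information checklist at the end of the document has a generic category, "Name of treatment provider", but whether it was ticked cannot be read in the available text, and it is not linked to the block or to any analysis.
- **Analysis.** Section 17.1: "Continuous outcomes will be compared between groups using 2-sample t-test or rank-sum tests according to the normality of the distribution". There is no operator term or stratum.

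**The concern.** Section 3.1 describes the lumbar plexus block (LPB) as the harder technique and the fascia iliaca block (FICB) as the simpler one. It would be natural for investigators to differ in speed, and for some to be more at ease with one block than the other. The person performing the block necessarily knows which one it is. The blinding in 6.1 covers the perioperative care teams.

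Randomising patients balances what is fixed before allocation. It does not balance a choice made afterwards in the light of the allocation. If the operator can be picked once the arm is known, the comparison in 17.1 estimates technique plus any difference in operator mix. At stake is whether the trial's one primary comparison can be read as a technique effect.

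A second, smaller matter applies even when operator choice is unrelated to arm: variation between operators stays in the error term and lowers precision.

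**Working it through.** **Inputs from section 12.2:** design difference 96 s, SD 128 s, 80% power, 95% confidence level, 29 per group, 70 enrolled.

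**Reproducing the plan's figure.** Standardised difference = 96 / 128 = 0.75. A two-sided two-sample t-test at 0.05 (noncentral t) needs 28.9, rounded up to 29 per group, with power 80.1%. The stated sample size reproduces and is not in question.

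**Inputs the documents do not give (assumptions).** Two operators whose mean times differ by D = 48, 96 or 128 s, with the same gap for both techniques. The slower operator's share of blocks differs between arms by 20 points (60% v 40%) or 40 points (70% v 30%).

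**Bias.** Spurious technique difference = D × difference in share.

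| Operator gap D | 20 points | 40 points |
|---|---|---|
| 48 s | 48 × 0.20 = 9.6 s (10% of 96 s) | 48 × 0.40 = 19.2 s (20%) |
| 96 s | 96 × 0.20 = 19.2 s (20%) | 96 × 0.40 = 38.4 s (40%) |
| 128 s | 128 × 0.20 = 25.6 s (27%) | 128 × 0.40 = 51.2 s (53%) |

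The sign depends on which arm the slower operator favours.

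**Type I error and power.** 20,000 simulated trials per scenario, 29 per arm, normal times. The total SD is held at 128 s for an even operator split, so the within-operator SD is √(128² − D²/4) = 125.7, 118.7 or 110.9 s. With no true technique difference, the unadjusted t-test rejects as follows.

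| Operator gap D | Same 50/50 mix in both arms | 20 points | 40 points |
|---|---|---|---|
| 48 s | 4.9% | 5.7% | 8.4% |
| 96 s | 5.0% | 8.9% | 20.8% |
| 128 s | 5.2% | 12.1% | 33.3% |

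With an operator term in the model, the rate is about 5% in every cell.

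**Precision when operator choice is independent of arm.** At a true difference of 96 s and a 50/50 mix, the unadjusted test has about 80% power. Adding operator gives about 81%, 85% and 90% for gaps of 48, 96 and 128 s.

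**Why adjustment alone is second best.** When the mix differs by 40 points, the adjusted analysis is unbiased in these simulations, but its power is 73%, 78% and 83% for the three gaps, against 81%, 85% and 90% when the mix is even. Keeping operator choice independent of arm avoids that loss.

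**The case against.** The strongest reply is that the documents are silent on operator choice rather than wrong about it. Nothing in them says or suggests that operators are chosen after allocation. If they are not, any imbalance is due to chance, and the t-test already allows for it. That stands. A reader might infer from 6.1 that the comparison is biased as planned, but the documents support only that independence is not secured.

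Three other strong readings also go too far.

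- *That the outcome is simply operator speed.* The endpoint is time to perform the technique, and the 6.1 interval includes positioning the patient for surgery, so only part of it reflects needle handling.
- *That operator and technique could never be separated afterwards.* The operators are study investigators and the procedure date is collected, so identity may be recoverable. Unless each operator does only one technique, it could then be added to a model. Separation fails only if operator is not recorded or is completely confounded with arm.
- *That any bias favours FICB.* If the investigator most at ease with LPB takes the LPB cases, LPB times shorten and the bias runs against the hypothesis in 2.2. The direction is unknown.

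It can also be said that a planning SD of 128 s may already contain operator variation, so that the power calculation has paid for it, and that power would be 87% if all 70 patients (35 per arm) were analysed. That is fair: the precision gain is a bonus, not a repair of a power deficit. Finally, blocked randomisation within operator could let an unblinded operator predict the next allocation. This is a sound objection to making stratification the main remedy.

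**Conclusion.** The concern holds in conditional form. The plan does not state that the operator is chosen independently of the allocation, does not list operator as a data item and does not use it in the analysis. If choice is independent of arm, validity is intact and the cost is some precision. If choice depends on the allocation, the technique difference is biased in an unknown direction. For assumed operator gaps of 48 to 128 s and share differences of 20 to 40 points, the bias is about 10 to 51 s, or 10% to 53% of the 96 s design effect, and the type I error about 6% to 33%.

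These sizes rest on two operators, a gap common to both techniques and normal times. None of them can be checked from the documents, and at the mild end the effect is slight. The conclusion that independence should be secured does not depend on the exact gap. This is a cheap improvement. It does not show that bias will occur, and it is no criticism of the sample size.

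**What to change.** 1. **Section 6.1:** require the operator to be named and recorded before the allocation is opened. Log any later change with its reason, and use the operator named beforehand in the analysis. This is the main step, because it makes operator a baseline characteristic.
2. **Section 6.4:** add operator ID (the person named and, if different, the person who performed the block).
3. **Section 17.1:** include the pre-named operator as a factor in the primary block-time comparison, pooling operators with very few cases under a rule set in advance. If a rank test is used, stratify it by operator (van Elteren). Tabulate block times by operator and technique.
4. **Optional:** stratify randomisation by operator, but only with concealed allocation and varying block sizes, and only if there are few enough operators to avoid very small strata.

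The cost is one data field, a few degrees of freedom and slightly less flexible scheduling. The sample size does not change.

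### The primary block time ends at surgical position and is recorded as one interval without that position, so block time and repositioning time cannot be separated afterwards.

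*Combined protocol and SAP*

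**What the plan says.** - **Objective (2.1):** "The primary objective will be to measure total time to perform the regional anesthesia technique". Section 4.1 lists the endpoint simply as the time for each block.
- **Clock stop (6.1):** timing is to "end when the need is withdrawn and the patient is positioned in the surgical positioning", where 'need' is evidently 'needle'. Section 6.2 agrees: the time "until the patient has been returned to the surgical position will be noted".
- **Needle sites (6.1, in the description of the dressings):** "in the back for the LP block and groin for the FICB".
- **Operations (6.1, repeated in 10.2):** patients "undergoing elective orthopedic surgical procedures involving the hip and upper thigh", with no limit on surgical position.
- **Allocation (6.1):** "Patients will be randomly divided into 2 groups: Group LP and Group FICB". No stratification is stated.
- **Data collected (6.4):** one block procedure time, in minutes and seconds. The operation is recorded. Needle-withdrawal time and surgical position are not listed.
- **Analysis (17.1):** a two-sample t-test or rank-sum test, with no adjustment.
- **Sample size (12.2):** a 96 s difference and a pooled SD of 128 s, taken from a study "investigating the time taken to perform 2 variations on the lumbar plexus block". Its clock definition is not given.

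**The concern.** The recorded interval has two parts: the time up to needle withdrawal, and the time from then until the child lies ready for surgery. The second part depends on the operation as well as the block. With one needle site in the back and the other in the groin, the move that follows may also differ by arm, in a direction set by the surgical position.

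Two things are at stake. The first is interpretation. Section 2.2 hypothesises that FICB is quicker to perform, yet a difference in the single interval could arise before needle withdrawal, after it, or both, and the data would not tell these apart. If repositioning differs by arm, the result also depends partly on this hospital's mix of surgical positions. The second is precision, because the planned test leaves a foreseeable source of variation unmodelled. A needle-withdrawal time that is not recorded in the operating room cannot be recovered later.

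**Working it through.** **1. The plan's own figure.** Inputs from 12.2: difference 96 s, SD 128 s, 95% confidence level, 80% power. Standardised difference = 96/128 = 0.75. A two-sided two-sample t-test at 0.05 (noncentral t) needs 28.9, so 29 per arm, with power 80.1%. With all 70 patients analysed (35 per arm) power is 87.1%. The stated figure reproduces.

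**2. Positioning as independent noise.** Assume that positioning adds a component independent of block time with SD s, that 128 s excludes it, and that the difference stays at 96 s. Then total SD = √(128² + s²). The documents give no value for s, so a range is shown.

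| Assumed s (s) | Total SD (s) | Power, 29 per arm | Power, 35 per arm |
|---|---|---|---|
| 0 | 128.0 | 80% | 87% |
| 30 | 131.5 | 78% | 85% |
| 60 | 141.4 | 72% | 80% |
| 90 | 156.5 | 63% | 72% |
| 120 | 175.5 | 54% | 62% |

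**3. Positioning as an arm-dependent turn.** Assume that a turn of T seconds is added after LPB when surgery is supine and after FICB when surgery is lateral, with a fraction q of operations lateral. Take 96 s as the difference without the turn. Then:

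- expected LPB minus FICB = 96 + T(1 − q) − Tq = 96 + T(1 − 2q)
- SD within each arm = √(128² + T²q(1 − q))

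At an assumed T = 90 s:

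| Lateral share q | Difference (s) | SD (s) | Power, 29 per arm |
|---|---|---|---|
| 20% | 96 + 54 = 150 | 133.0 | 99% |
| 50% | 96 + 0 = 96 | 135.7 | 75% |
| 80% | 96 − 54 = 42 | 133.0 | 22% |

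At an assumed T = 120 s, the expected difference runs from 96 + 120 = 216 s (all supine) to 96 − 120 = −24 s (all lateral).

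**4. Reading the two together.** Step 2 can only lower power, because it fixes the difference. Step 3 moves power either way, because the difference itself moves. The documents give no surgical positions, case mix or turning times, so they cannot say which pattern applies or how strongly.

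**The case against.** The strongest reply is that the clock stop is deliberate. The objective is total time, section 3.1 calls LPB time-consuming, and section 3.2 hopes that FICB is more expeditious. Getting the child back into position is part of the operating-room time a block costs. This stands: counting positioning is not an error, and making needle withdrawal the primary endpoint would change the sponsor's question.

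The arm-by-position mechanism is an inference from the two needle sites; no block position or surgical position is stated. Section 6.1 also puts dressings at both sites in every child without saying when. If both go on before final positioning, repositioning may be similar in the two arms and the formula in step 3 would not hold. This also stands. It limits what can be said about size, but does not make the single interval separable.

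Randomisation balances surgical position in expectation, so there is no confounding. The operation is recorded and may serve as a partial proxy for position. Both are correct, but the proxy does not supply the missing time stamp.

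Two stronger readings are tempting, and the documents support neither:

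- **The stated 80% power is eroded.** Section 12.2 does not define the earlier study's clock, so 128 s may already include positioning. Step 3 also shows that power could rise.
- **Waiting for staff inflates the outcome.** Section 6.1 does say "The team providing intraoperative care will step out of the room during the regional block", but it also says that the research team, with an attending anesthesiologist, gives care meanwhile. Nothing says that positioning waits for the other team.

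**Conclusion.** The point holds as a limit on interpretation and a missed gain in precision. It shows neither bias nor an error in the sample size, whose arithmetic reproduces. On the text alone, the primary interval includes repositioning, only that interval is collected, surgical position is not among the listed data, and the comparison is unadjusted. How much a result owes to repositioning therefore could not be determined.

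The size is unknown. The 72% to 54% range at 29 per arm rests on an assumed independent positioning SD of 60 to 120 s, with the difference fixed at 96 s and 128 s excluding positioning. The 99% to 22% range rests on an assumed 90 s turn and 20% to 80% lateral operations. Both are illustrations, not estimates. The effect would be small if nearly all operations share one position or if positioning is quick. The remedy is a cheap improvement and does not require a change of primary endpoint.

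**What to change.** - Keep total time to surgical position as the primary outcome.
- In 6.1, 6.2 and 6.4, add a second time stamp at needle withdrawal, and pre-specify time to needle withdrawal as a supporting analysis. The difference between the two stamps gives the time after the needle. The supporting measure still includes any turn into the block position made after the clock starts, and the report should say so.
- In 6.4, record planned surgical position before allocation.
- In 17.1, adjust the primary comparison for planned surgical position, and report the arm difference by position. Both are needed: a common adjustment removes variation that position adds equally to both arms, while only the by-position results show a turn that differs by arm. With 70 patients, the by-position results are descriptive.

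The cost is one time stamp, one baseline item and slightly more analysis. Clinical care and the enrolment target do not change.

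### Opioid use, pain and length of stay are compared across mixed hip and upper-thigh operations without stratifying by or adjusting for the operation, which gives up precision on the secondary outcomes at almost no saving.

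*Combined protocol and SAP*

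**What the plan says.** Sections 6.1 and 10.2 define the population by age, ASA grade and site of surgery: children "undergoing elective orthopedic surgical procedures involving the hip and upper thigh". Neither section restricts the kind or extent of operation.

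Allocation is described in one sentence of section 6.1: "Patients will be randomly divided into 2 groups: Group LP and Group FICB". It mentions no stratification factor, block or minimisation.

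Section 17.1 holds the whole analysis plan. "Continuous outcomes will be compared between groups using 2-sample t-test or rank-sum tests according to the normality of the distribution", and "Categorical outcomes will be compared between groups using Chi-square or Fisher's exact tests, according to cell size". No comparison contains a covariate or stratum.

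The operation is collected. Section 6.4 lists "primary diagnosis, list of comorbidities, procedure, date, duration, admission status intraoperative medications", but no analysis uses these items. Section 10.1 says that candidates are found on the surgery schedule, so the planned operation is known before allocation.

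The outcomes concerned are the secondary ones of section 2.1: "opioid consumption during the first 24 and 48 postoperative hours, pain scores during the first 24 and 48 hours, and hospital length of stay". Section 2.2 hypothesises that the two blocks relieve pain equally well, and section 3.2 rests the case for the fascia iliaca block on that result. No margin is given.

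**The concern.** Opioid use, pain and length of stay may plausibly differ by operation. If they do, an analysis that ignores the operation leaves that variation in the residual error of every analgesic and length-of-stay comparison. With about 35 children per arm, unstratified allocation can also leave one arm with noticeably more of the heavier operations, and an unadjusted test does not correct for this.

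The direction of the loss matters. The analgesic hypothesis is one of equality without a margin, and the sample size in section 12.2 rests on block time alone. Wide intervals make a non-significant result more likely, and such a result could be read as support for equal analgesia. Sections 6.2 and 6.3 standardise the anaesthetic and the postoperative regimen, which limits other sources of variation. The operation is a remaining source that the plan records but does not use.

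**Working it through.** **The plan's own figure.** Section 12.2 gives a difference of 96 s, SD 128 s, 80% power and 95% confidence. The standardised difference is 96/128 = 0.75. A two-sided two-sample t-test at 0.05 needs 28.9, so 29 per group, with power 80.1%. The stated figure reproduces. It concerns block time and is not affected by what follows.

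**Inputs for the secondary outcomes.** From the plan: 70 children, so 35 per arm if allocation is 1:1. Assumed, because the documents do not give them:
- the share R² of within-arm variance explained by a two-level operation class: 10%, 20% or 30%;
- the prevalence p of the heavier class: 30% to 50%.

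**Precision.** The 95% CI half-width in SD units is about t × √((2/35)(1 − R²)), with t = 1.995 on 68 degrees of freedom. At R² = 0 this is 1.995 × 0.239 = 0.477. The equivalent unadjusted trial size is 70/(1 − R²). The smallest difference detectable with 80% power is 0.68 SD unadjusted and scales by √(1 − R²). The formula ignores the one degree of freedom lost to the extra term, which is negligible here.

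| R² | Half-width (SD) | Equivalent N | Detectable difference (SD) | Power for 0.5 SD |
|---|---|---|---|---|
| 0 | 0.477 | 70 | 0.68 | 54% |
| 0.1 | 0.453 | 78 | 0.64 | 58% |
| 0.2 | 0.427 | 88 | 0.61 | 64% |
| 0.3 | 0.399 | 100 | 0.57 | 69% |

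**Chance imbalance.** At 35 per arm, 20 percentage points is 7 children (7/35). With two independent Bin(35, p) counts, the probability of a difference at least that large is 8.9% at p = 0.3, 11.2% at p = 0.4 and 12.0% at p = 0.5.

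**What such an imbalance does.** A 20-point imbalance shifts the contrast by 0.20 × √(R²/(p(1 − p))) SD:
- R² = 0.2, p = 0.5: 0.20 × √(0.2/0.25) = 0.18 SD
- R² = 0.3, p = 0.3: 0.20 × √(0.3/0.21) = 0.24 SD

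The other combinations of R² 0.2 to 0.3 and p 0.3 to 0.5 lie between these. The shift is at most half of the unadjusted half-width (0.24/0.477 = 0.50).

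**Type I error and power by simulation.** Each setting used 20,000 trials with 35 per arm, p of 0.3 or 0.5, and the heavier class 1.0 or 1.5 within-class SD worse (R² 0.17 to 0.36).
- No block effect, all randomisations: the unadjusted test rejects in 4.7% to 5.3%.
- No block effect, only trials imbalanced by 20 points or more: 12% to 20% unadjusted, 4% to 5% adjusted.
- True effect of 0.6 within-class SD, all randomisations: power is 51% to 61% unadjusted, 68% to 69% adjusted.

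**The case against.** The strongest answer is that nothing here is an error. After randomisation an unadjusted two-group test is valid, and its 5% level and confidence interval already allow for chance imbalance. A reader might infer that mixing operations inflates the false-positive rate or biases the trial. The documents do not support that: the simulated type I error is 4.7% to 5.3%, and extra residual variance cannot by itself create a difference. The 12% to 20% rejection rate applies only within the roughly one trial in ten that is badly imbalanced. This part of the objection stands in full.

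A reader might also take it as given that the operations run from minor to major and strongly determine analgesic need. The documents list no operations and give no variance figures. Some text suggests a narrower mix: participation of about 48 hours to discharge, ward pain scores over 48 hours, and scheduled intravenous analgesics. On the other side, section 6.4 also collects admission status and discharge destination. The spread is therefore an assumption, and at R² = 0.1 the gain is only 0.02 SD in half-width.

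It is also fair that these outcomes are secondary and that no power is claimed for them. Age, which ranges from 2 to 18 years and bears on the choice of pain scale, is another candidate covariate. Neither point argues against using the operation. A valid test can still be needlessly imprecise, and the variable is already collected.

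**Conclusion.** The point holds as a cheap improvement in precision. It does not show that the planned tests are invalid. The primary block-time comparison and its 29 per group stand.

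For opioid use, pain and length of stay, adjusting for operation class would narrow the 95% CI half-width from 0.48 SD to 0.45, 0.43 or 0.40 SD at 10%, 20% or 30% of variance explained. With 30% to 50% heavier operations, an imbalance of 20 points or more arises in 9% to 12% of trials. At 20% to 30% of variance explained, a 20-point imbalance moves the contrast by 0.18 to 0.24 SD, too little on its own to make a null comparison significant. All of these sizes rest on an assumed case mix and prognostic strength. What the text itself establishes is that eligibility is broad, no stratification is named, every comparison is unadjusted, and the procedure is recorded without being used.

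The gain is worth having because the secondary outcomes carry the equality half of the hypothesis, where wide intervals are easily misread.

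**What to change.** In section 17.1, compare opioid use, length of stay and pain (as one summary score per patient) between arms with a linear model containing arm and a two-level operation class. Define the class before unblinding, from the scheduled operation, for example major bone surgery versus other. Report the adjusted difference with its 95% CI. Where the plan would use ranks, take the p-value from the stratified (van Elteren) rank-sum test.

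If enrolment has not started, also state in section 6.1 that permuted-block randomisation is stratified by the same class. If it has started, the analysis change alone still recovers precision and removes the effect of imbalance in that class.

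The cost is one extra model term and two allocation lists instead of one. No sample size, eligibility rule or treatment changes. There are three drawbacks. The class must be defined in advance and, for stratification, assigned before allocation. The van Elteren test gives no effect estimate, so where ranks are used the p-value and the interval come from different methods. A summary pain score also does not settle how the three pain scales in section 6.4 are to be combined, which needs its own rule.
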